#### Planned Dose and Overdose

The body weight-based planned dose was calculated based on most recent weight of previous visits. When calculating the planned dose, the body weight is rounded to a single decimal using conventional rounding rules. While in preparing actual dose, an unconventional rule is applied for calculating the volume of the concentrated drug (50 mg/mL) in milliliter. Any volume of 0.1 or above is rounded up (e.g. 25.14 mL is rounded up to 26 mL) and any volume below 0.1 is rounded down (e.g. 25.09 mL is round up to 25 mL. The overdose is defined as any actual dose >10% above the planned body weight-based dose.

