- b Patients not previously genotyped may beconsented and havegenotypeperformed as part of the study. Oncethe genotype is con firmed, all additional screening procedures will be performed -2 weeks from Week 1/Baseline. Patients may be enrolled in the study based on historical DNA test results; however, a blood sample for DNA testing will be obtained on all patients to confirm DMD mutation(s). In addition, a second blood sample will be obtained for genotyping of LTBP4 and SPP-1. So that total blood volume taken for the Screening visit does not exceed recommendations, theblood sample for DMD genotyping may be drawn at any time prior to the Week 2 visit and theblood sample for LTBP4 and SPP-1 may be drawn at any timeduring the dose-titration period. If the confirmatory DNA sample is negative for DMD on any enrolled patient, that patient will be withdrawn from the study.
- ^c Clinical safety laboratory assessments (blood chemistry [including liver function], renal function, hematology [including pla telets], and coagulation) must be obtained with results available within 2 weeks prior to dosing. (See Section 10.3.5 for the list of tests to be completed.)
- ^d Pla sma PK samples will be collected pre-dose, immediately prior to the end of infusion (prior to flush) and approximately 1-3 hours and 6-8 hours after completion of study drug infusion. Urine PK will be collected over the first 4 hours after start of infusion.
- ^c Vital signs include blood pressure, heart rate, respiration, and temperature. On infusion days, vital signs will be measured within 60 minutes prior to infusion, within 5 minutes (±2) after the end of infusion, and at 30 minutes (±5), and 60 minutes (±10) after the end of the infusion. All assessments will be performed after patients have remained calm for 5 minutes. Pulse rate and respiratory rate should be measured over 1 minute.
- ^f Weight will be measured prior to study drug infusions at thespecified visits.
- ^g Height/length will be measured as part of every physical examination. The examination will include general appearance; head, ears, eyes, nose, and throat; heart; lungs; chest; abdomen; skin; lymph nodes; musculoskeletal; and neurological systems.
- A 2-week window is allowed in the event the child is unable to complete this assessment at a given visit.
- Only performed in patients 36 months of age and older

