9.2. Treatments Administered

Eligible patients will receive a once weekly IV infusion of eteplirsen for up to 96 weeks. Eteplirsen should be prepared for dosing by following the steps detailed in the study-specific Pharmacy Manual.

The starting dose is 2 mg/kg eteplirsen, with escalation to 4, 10, 20, and 30 mg/kg over the course of the dose-titration period.

The following guidelines for the timing of dosing should be followed throughout the study:

- Patients should receive Eteplirsen once every 7 days starting on Week 1. A window of ± 3 days from the scheduled dose is acceptable after the first infusion.
- Patients may not receive 2 separate doses of Eteplirsen within the same 60-hour period.
- The Medical Monitor should be contacted in the event of ≥2 consecutive missed doses.

The administered dose is calculated by patient weight, which will be collected on a weekly basis and used to calculate the dose to be administered at the next visit(s). For example, the weight collected at Week 2 will be used to calculate the doses to be infused during the Week 3 visit.

Eteplirsen should be diluted in a normal saline, where the final volume, after eteplirsen has been added, equals the volume appropriate for the patient's weight. The drug delivery bag, syringe or flask is to be labeled in accordance with standard pharmacy practice and to include total volume as well as drug dose in milligrams. Eteplirsen will be diluted in normal saline to a total volume per Table 5 and infused IV for approximately 35 to 60 minutes using an infusion or syringe

pump. It is recommended that a topical anesthetic cream be applied to the infusion site prior to each administration of eteplirsen.

Table 5: Example Eteplirsen Dilution Scheme

Patient Weight	Total Eteplirsen Dose (30 mg/kg)	Total Volume of Eteplirsen Drug Product	Dilution in Saline up to Total Volume of:	Maximum Eteplirsen Concentration in Infusion
<5 kg	<150 mg	<3 mL	10 mL	15 mg/mL
5 to 10 kg	150 to 300 mg	3 to 6 mL	15 mL	20 mg/mL
10 to 15 kg	300 to 450 mg	6 to 9 mL	25 mL	18 mg/mL
15 to 25 kg	450 to 750 mg	9 to 15 mL	50 mL	15 mg/mL
>25 kg	>750 mg	>15 mL	100 mL	

Note: Refer to the Pharmacy Manual for other dosing dilution schemes.

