11.6. Special Situations

11.6.1. **Overdose**

An overdose is defined as administration of a dose that is >10% higher than the assigned dose per the protocol. An overdose is not an AE. An overdose will be reported even if it does not result in an AE. An overdose will be recorded on the appropriate form and sent to the Sponsor or designee within 24 hours.

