## 6.7. Exposure to Study Drug

The exposure to eteplirsen will be summarized for eteplirsen-treated patients in the Safety Analysis Set. The variables will include the following (as applicable): total number of infusions received, total number of infusions on 30 mg/kg of eteplirsen received, cumulative amount of drug received (mg), duration on eteplirsen in 24-week intervals, and patient years on eteplirsen. For both the 4658-102 final analyses, these endpoints will be calculated cumulatively

Patient-level study drug information will be provided in a data listing. Additionally, a listing of the derived exposure parameters above will be generated as well as a listing of overdoses. The actual dose will be compared to the planned dose. Any actual dose that is greater than 1.10 times of the planned dose will be considered an overdose. Planned dose is calculated as the dose level in mg/kg multiplied by the patient's most recent weight prior to the dose (or on the same day with no time).

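### Read literally, the SAP's whole-millilitre preparation rule produces overdoses by the plan's own >10% definition (at 2 mg/kg, every weight from 5.0 to 22.7 kg), and the overdose flag has two different weight definitions

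*SAP*

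**What the plan says.** SAP 5.7 (Planned Dose and Overdose) takes the planned dose from the latest weight at an earlier visit, rounded to 0.1 kg. For the prepared dose it rounds the volume of 50 mg/mL concentrate: "Any volume of 0.1 or above is rounded up (e.g. 25.14 mL is rounded up to 26 mL". A fraction below 0.1 mL goes down; the second example takes 25.09 mL to 25 mL (its text says up where the result is down). Both examples end in whole millilitres. The paragraph closes: "The overdose is defined as any actual dose >10% above the planned body weight-based dose".

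The same threshold appears twice more. SAP 6.7: "Any actual dose that is greater than 1.10 times of the planned dose will be considered an overdose". Protocol 11.6.1: "An overdose is defined as administration of a dose that is >10% higher than the assigned dose per the protocol"; that section also requires each overdose to be sent to the sponsor or designee within 24 hours, whether or not an adverse event follows.

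Protocol 9.2 sets distinct titration steps: "The starting dose is 2 mg/kg eteplirsen, with escalation to 4, 10, 20, and 30 mg/kg over the course of the dose-titration period". It also carries the weight forward from the previous visit: "the weight collected at Week 2 will be used to calculate the doses to be infused during the Week 3 visit". SAP 6.7 instead uses the "most recent weight prior to the dose (or on the same day with no time" recorded), and Table 2 footnote f of the protocol states: "Weight will be measured prior to study drug infusions".

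Neither SAP section exempts rounding from the overdose definition or limits the rounding rule to particular weights or dose levels.

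**The concern.** At the SAP's example volume, rounding is harmless: 26/25.14 is +3.4%. But 25.14 mL is 1,257 mg, or about 42 kg at 30 mg/kg, well above the 15 to 25 kg band of Protocol Table 5. For patients of 5 to 25 kg on 2 to 30 mg/kg, planned volumes run from 0.2 to 15 mL, so one 50 mg step can be a large part of the dose, or several times the dose.

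Three outputs depend on this:

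- **Overdose listing (SAP 6.7).** If sites used the rule, correctly prepared doses and real errors would be listed together, each with a 24-hour report. With about 12 patients, all weighing 5.0 to 22.7 kg, all 12 × 2 = 24 scheduled 2 mg/kg infusions would qualify.
- **PK.** Week 2 (2 mg/kg) is a PK visit, and both documents plan a dose-proportionality evaluation without saying whether nominal or actual dose enters it.
- **Safety by titration step.** Two nominal steps could be the same dose in milligrams.

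Separately, two weight definitions let the same infusion be an overdose under one SAP section and not under the other.

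**Working it through.** **Inputs.** Concentration 50 mg/mL (Protocol 9.1, SAP 5.7); dose levels D = 2, 4, 10, 20, 30 mg/kg (Protocol 9.2); weight w in 0.1 kg steps and the rounding rule (SAP 5.7); limit 1.10 × planned (SAP 5.7, SAP 6.7, Protocol 11.6.1). The documents give no weight distribution. The 5 to 25 kg range follows the Table 5 bands and 5 to 10 kg the Table 6 weights; 7 to 18 kg and 15 to 25 kg are assumptions.

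**Formulas.** Planned volume V = D × w / 50. Rounded volume R = whole part of V if the fraction is below 0.1, otherwise the next whole number. Over the limit if 50R > 1.10 × D × w.

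**The SAP's own examples.** 25.14 has fraction 0.14, so R = 26; 25.09 has fraction 0.09, so R = 25. Both reproduce.

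**2 mg/kg.** From 5.0 kg to just under 25 kg, V lies between 0.2 and 1 mL, so R = 1 and the dose is 50 mg. It exceeds the limit when 50 > 2.2w, that is w < 22.73 kg. At 10 kg: 50/20 = 2.5 (+150%). At 22.7 kg: 50/45.4 = 1.101. At 22.8 kg: 50/45.6 = 1.096, within the limit.

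**2 against 4 mg/kg.** At 4 mg/kg, V = 0.08w and R = 1 while V < 1.1, that is w < 13.75 kg. So both steps give 50 mg from 5.0 to 13.7 kg. At 13.8 kg, V = 1.104 and R = 2 (100 mg).

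**30 mg/kg.** V = 0.6w. A volume rounded up to n mL exceeds the limit when n − 0.9 ≤ V < n/1.1, which is possible only for n ≤ 9. The affected weights are 5.2–6.0, 6.9–7.5, 8.5–9.0, 10.2–10.6, 11.9–12.1 and 13.5–13.6 kg: 32 of 201 weights from 5 to 25 kg, none from 13.7 kg up.

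**Share of weights over the limit** (each 0.1 kg counted equally), and share of scheduled infusions = (2 × the sum of the shares at 2, 4, 10 and 20 mg/kg + 40 or 88 × the share at 30 mg/kg) / 48 or 96:

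| Range (kg) | 2 | 4 | 10 | 20 | 30 mg/kg | 48 wk | 96 wk |
|---|---|---|---|---|---|---|---|
| 5–25 | 89% | 77% | 59% | 31% | 16% | 23.9% | 19.9% |
| 5–10 | 100% | 100% | 71% | 57% | 43% | 49.6% | 46.4% |
| 7–18 | 100% | 78% | 71% | 39% | 20% | 28.5% | 24.2% |
| 15–25 | 77% | 77% | 50% | 13% | 0% | 9.0% | 4.5% |

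For 5–25 kg at 48 weeks: (2 × (0.886 + 0.766 + 0.587 + 0.308) + 40 × 0.159)/48 = 0.239.

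**Dose proportionality.** Suppose exposure is exactly proportional to actual dose, and log exposure is regressed on log nominal dose at the PK levels 2, 10, 20 and 30 mg/kg. At 10 kg the rounded doses are 50, 100, 200 and 300 mg, or 5, 10, 20 and 30 mg/kg, and the slope is 0.64 instead of 1. At 7, 12, 15 and 18 kg it is 0.56, 0.75, 0.80 and 0.89.

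**Weight definition.** Previous-visit weight 12.0 kg at 30 mg/kg: V = 7.2 mL, R = 8 mL, 400 mg. Under SAP 5.7, 400/360 = 1.111, an overdose. With a same-day weight of 12.2 kg under SAP 6.7, 400/366 = 1.093, not an overdose.

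**The case against.** The strongest objection is that the protocol delegates preparation to the Pharmacy Manual, which is not available. The SAP describes pharmacy practice second-hand, its examples fit heavier patients, and Protocol Table 5 shows unrounded volumes. This stands as a limit on what can be concluded: nothing here shows that any child received a rounded dose. It does not remove the fault, because if sites did not use the rule, SAP 5.7 misstates how the actual dose arises. Nor does a finer reading rescue the text: rounding up to the next 0.1 mL contradicts both examples and still exceeds the limit at some weights at 2 and 4 mg/kg, though at none at 10 to 30 mg/kg.

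Second, the >10% figure defines what is reported and does not cap preparation, so rule and threshold can formally coexist. That is true, but the listing then no longer separates errors from routine preparation. It is also true that from 22.8 to 25.0 kg no dose level exceeds 10%.

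Third, the infusion shares hold weight fixed in growing children, and the 5 to 10 kg row comes from a blood-volume table and is unlikely to describe a trial in which about half the patients are 24 to 48 months old. With assumed linear growth over 96 weeks, the share is about 8% (12 to 17 kg), 4% (14 to 19 kg) or 24% (9 to 14 kg). The shares are therefore illustrative only.

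Fourth, the PK effect needs the literal rule, nominal dose in the analysis and proportional exposure together, and it comes mainly from the 2 mg/kg point: on 10 to 30 mg/kg alone the slope is 1.00 at 10 kg and at 15 kg. This stands as a condition on that part. The 2 mg/kg level is nevertheless named in the secondary objective.

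**Conclusion.** The concern holds. As written, SAP 5.7's rule produces doses that SAP 5.7, SAP 6.7 and Protocol 11.6.1 call overdoses, and it removes the difference between the first two titration steps of Protocol 9.2 up to 13.7 kg. The 2 mg/kg result is exact for each weight from 5.0 to 22.7 kg and needs no weight distribution; the 30 mg/kg effect is confined to six narrow bands below 13.7 kg. These results rest on the literal whole-millilitre reading, which both SAP examples support. How many infusions would be flagged depends on unknown weights and cannot be fixed from the documents. The slope of 0.56 to 0.89 for 7 to 18 kg applies only if nominal dose is used and exposure is truly proportional to actual dose. The mismatch in weight definition between SAP 5.7 and 6.7 stands whether or not the rounding rule was used.

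**What to change.** Before analysis:

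1. Reconcile SAP 5.7 with SAP 6.7, Protocol 9.2, Protocol 11.6.1 and the Pharmacy Manual, so that the text states how the dose was actually prepared. Which preparation rule applies is not a matter for this review.
2. Derive actual milligrams from the recorded administered volume, and summarise actual mg/kg at each nominal dose level.
3. State one weight for the planned dose, and use it in both SAP 5.7 and 6.7 for the overdose flag.
4. Keep the overdose listing, but show exceedances explained by volume rounding separately from other overdoses.
5. State in SAP 6.10 that actual dose is used for dose-normalised PK and dose proportionality.

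The cost is SAP wording, a check against the Pharmacy Manual, one derived variable and one table. Protocol 13.7 already plans to summarise administered volume, and SAP 6.7 already compares actual with planned dose.

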#### Patient Years on Eteplirsen

The patient years on eteplirsen will be calculated as (Last Treatment Date - First Treatment Date + 7)/365.25.

#### **Baseline Visit**

Baseline visit in Study 4658-102 will be considered the last visit prior to the initiation of eteplirsen in Study 4658-102.

#### Change from Baseline

Change from Baseline will be calculated as follows:

*Change from Baseline = Post-Baseline Value – Baseline Value* 

The change may be classified into a categorical variable, as appropriate.

#### Percent Change from Baseline

Percent change from Baseline will be calculated as follows:

*Percent change from Baseline = (Change from Baseline / Baseline Value)\*100* Percent change from Baseline will not be calculated if Baseline value is 0.

Sarepta Therapeutics, Inc. Protocol 4658-102	
	Statistical Analysis Plan for Final Analysis

#### Treatment-emergent Adverse Event (TEAE)

An AE will be considered treatment-emergent if it starts in the time period starting with the initiation of the first dose of eteplirsen and ending 28 days after the last dose of eteplirsen.

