Patients will be evaluated for inclusion during the Screening Period of up to 2 weeks to ensure eligibility prior to dosing with eteplirsen. After obtaining informed consent, screening assessments will include a review of inclusion/exclusion eligibility criteria, demographics and medical history, previous and current medications, clinical safety laboratory testing (blood and urine samples), vital signs, physical examination (including height/length and weight), 12-lead electrocardiogram (ECG), and echocardiogram (ECHO). Blood samples for the screening clinical safety laboratory assessments must be obtained within 2 weeks prior to the Baseline/Week 1 visit, and results must be available prior to dosing at Baseline/Week 1. A blood sample to confirm DMD genotype will also be obtained. Patients not previously genotyped may be consented and have genotype performed as part of the study. Once the genotype is confirmed, all additional screening procedures will be performed 2 weeks from Week 1/Baseline. The sample for genotyping can be drawn at Screening or any time prior to the Week 2 visit so that total blood volume taken for the Screening visit does not exceed recommendations. A separate blood sample will be obtained for genotyping of latent transforming growth factor beta (TGF) binding protein 4 (LTBP4) and secreted phosphoprotein 1 (SPP-1); this may be drawn at any time during the dose-titration period.

NAME OF COMPANY

Sarepta Therapeutics Inc. [name]

[contact]

NAME OF FINISHED PRODUCT

Eteplirsen Injection

NAME OF ACTIVE INGREDIENT

Eteplirsen

Treatment Period

Patients will be enrolled into 1 of 2 age cohorts. Cohort 1 will include approximately 6 patients ages 24 to 48 months old and Cohort 2 will include approximately 6 patients ages 6 to <24 months old. Cohort 1 will be enrolled first, and only after the first 3 patients in Cohort 1 have completed at least 12 infusions of eteplirsen and all available safety data have been reviewed will enrollment begin for patients in Cohort 2. An external Data Monitoring Committee (DMC) will review safety data at least weekly through the first 12 weeks of dosing for the first 3 patients of each age cohort. Reviews will be at least quarterly thereafter.

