10.2.4. Other Assessments

Screening will also include clinical safety laboratory assessments, vital signs, physical examination, height/length and weight, a 12-lead ECG, an ECHO, assessment of previous and current medications/therapies, assessment of pre-treatment AEs,

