11. ADVERSE EVENTS

11.1. Collection of Adverse Events

Over the entire duration of the study, site personnel will ensure that all AEs are recorded appropriately. If an AE occurs, the primary concern is for patient safety, and the Investigator will use professional judgment and expertise to determine the appropriate course of action.

All AEs from the time of informed consent through the safety follow-up visit (which will occur approximately 4 weeks after the last infusion regardless of the patient's duration in the study) will be recorded in each individual patient's electronic case report form (eCRF). If at any time after the patient has completed participation in the study, the Investigator or study staff becomes aware of a SAE that the Investigator believes is related to the IP (Section 11.3.1) or is related to a study procedure (Section 11.3.2), then the event and any known details must be reported promptly to the Sponsor.

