11.2. Definition of Adverse Events

11.2.1. Adverse Event

An AE is any untoward medical occurrence in a clinical trial participant, which does not necessarily have a causal relationship with the investigational drug. An AE can, therefore, be any unfavorable and unintended symptom, sign, disease, condition, or test abnormality that occurs during or after administration of an IP whether or not considered related to the IP. Adverse events include:

- Symptoms described by the patient or signs observed by the Investigator or medical staff.
- Test abnormalities (laboratory tests, ECG, X-rays, etc.) that result in an alteration in medical care (diagnostic or therapeutic).

Abnormalities present at baseline are considered AEs only if they reoccur after resolution or worsen during the AE collection period.

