## 5.2.6 Handling of Incomplete Dates

An incomplete date will occur when the exact date an event occurred or ended cannot be obtained for a patient. Incomplete dates will be imputed as described below. No other imputation of missing data will be performed.

- For a partial or missing medication date, the medication will be classified as a concomitant medication unless the available part of the date indicates it is impossible for the drug to be concomitant. For example, if only the year for the stop date is available and the year is prior to the year of dosing, the medication will be classified as a prior medication.
- For a partial or missing AE onset date, the event will be classified as treatment emergent if the month and/or year of the onset date are on or after the initiation of eteplirsen and within 28 days of the last dose of eteplirsen. If a partial AE onset

Statistical Analysis Plan for Final Analysis

date is after the treatment end date, then the date will be imputed as the first day of the month.

• For the purpose of calculating the time since DMD diagnosis or duration of prior corticosteroid use, if the date of DMD diagnosis or the start date of corticosteroid use has a missing day but known month and year, then the 15th of the month will be used in the calculation. If the date has a missing day and month and only the year is known, December 31st of the recorded year will be used in the calculation.

In all cases, the original missing or incomplete dates will be presented in the data listings.

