#### Treatment-Emergent Laboratory, Vital Signs, ECGs, and ECHO Abnormality

A treatment-emergent laboratory, vital signs, ECGs, and ECHO abnormality will be defined as any laboratory, vital signs, ECGs, and ECHO abnormality occurring or worsening after the initiation of eteplirsen dosing and within 28 days of the last dose of eteplirsen.

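### The SAP classifies AEs as treatment-emergent by start date alone, so a pre-dose AE that worsens on eteplirsen can drop out of the TEAE tables

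*SAP*

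**What the plan says.** **TEAE rule.** In SAP section 5.7, "An AE will be considered treatment-emergent if it starts in the time period starting with the initiation of the first dose of eteplirsen"; the window closes 28 days after the last dose. SAP section 5.2.6 handles partial onset dates on the same principle: "the event will be classified as treatment emergent if the month and/or year of the onset date are on or after the initiation of eteplirsen". The protocol uses the term TEAE but gives no definition that adds worsening.

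**Rule for measured abnormalities.** Later in section 5.7, a treatment-emergent laboratory, vital-sign, ECG or ECHO finding is any "abnormality occurring or worsening after the initiation of eteplirsen dosing and within 28 days of the last dose of eteplirsen".

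**Collection.** Protocol section 11.1 records "All AEs from the time of informed consent through the safety follow-up visit", and the screening assessments in section 10.2.4 include "assessment of pre-treatment AEs". Screening lasts up to 2 weeks. The synopsis adds "Patients not previously genotyped may be consented and have genotype performed as part of the study", with the remaining screening procedures following once genotype is confirmed, so the time from consent to first dose can exceed 2 weeks.

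**Worsening as an AE.** Protocol section 11.2.1 says: "Abnormalities present at baseline are considered AEs only if they reoccur after resolution or worsen during the AE collection period". It does not say what onset date such an AE receives. Section 11.4 asks for one onset and one resolution per event, and does not say that a worsening closes one record or opens another.

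**Tabulation.** Protocol section 13.8.2.1 and SAP section 6.8.1 tabulate TEAEs and send other AEs to listings. Both also summarise all SAEs whatever their treatment-emergent status.

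**The concern.** AE incidence is the first component of the primary endpoint, and the study has no control arm. The TEAE tables are therefore the main summary of what happened to these children on drug. Aggravation of an event already present at the first dose is part of that picture. A mild gastrointestinal or respiratory illness that begins in screening and becomes severe on eteplirsen is an example.

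Under a start-date rule, such an event can be classed with pre-treatment events even if the investigator attributes the worsening to the drug. SAP section 5.7 would then call it treatment-related, yet the treatment-related tables in section 6.8.1 are restricted to TEAEs and would omit it. The SAP gives no reason for counting worsening in measured abnormalities but not in clinical AEs.

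**Working it through.** The plan states no figure to reproduce. The check has two parts: apply the rule as written and with a worsening clause, then size the effect of one reclassified child.

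**1. Rule check.** Study days follow SAP section 5.7, with the first dose on Day 1. For a child treated weekly to Week 96, the last dose falls on Day (96 − 1) × 7 + 1 = 666 and the window closes on Day 666 + 28 = 694.

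- SAP rule: TEAE if 1 ≤ onset day ≤ 694.
- Rule with worsening: TEAE if the SAP rule holds, or if 1 ≤ worsening day ≤ 694.

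| Case | SAP rule | With worsening |
|---|---|---|
| Onset Day −7, worsens Day 30, one record | not a TEAE | TEAE |
| Onset Day −7, no worsening | not a TEAE | not a TEAE |
| Onset Day 30 | TEAE | TEAE |
| Worsening entered as a new AE dated Day 30 | TEAE | TEAE |

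The rules differ only in the first case. The last row shows that the outcome turns on how the site enters the worsening.

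**2. Where the first case appears.** From SAP sections 6.8.1 and 6.8.2:

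- Left out: all TEAE tables, including TEAEs by severity, treatment-related TEAEs, treatment-emergent SAEs, TEAEs leading to discontinuation and TEAEs of special interest.
- Kept: the listing of non-treatment-emergent AEs and, if serious, the SAE listing and the all-SAE summary.

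**3. Size.** The planned numbers are about 12 children, about 6 per cohort. SAP section 6.8.1 counts a child once per preferred term, so the unit is the child in a given row. One reclassified child moves that row by at most 1/n:

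- Overall: 1/12 = 8.3 percentage points.
- Within a cohort: 1/6 = 16.7 percentage points.

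The shift is zero if the child already counts in the row through another AE. The SAP plans no intervals for these rates. For scale only, exact (Clopper-Pearson) 95% limits are:

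- 0/12: 0 to 26.5%; 1/12: 0.2 to 38.5%.
- 0/6: 0 to 45.9%; 1/6: 0.4 to 64.1%.

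The documents do not say how many AEs to expect between consent and first dose, or how many would worsen, so no expected count can be computed.

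**The case against.** A reader might infer that these events vanish from every AE table, serious ones included. The documents do not support that. Both the protocol and the SAP summarise all SAEs regardless of treatment-emergent status, so a pre-dose AE that becomes serious is still tabulated there. Non-serious ones are still listed, and with about 12 children that listing can be read line by line.

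A reader might also take it as settled that a worsened AE keeps its pre-dose onset date. Nothing says so. Protocol section 11.2.1 makes worsening of a baseline abnormality an AE, which could be read as an event arising at the worsening and hence a TEAE. SAP section 6.8.1 allows for several episodes of one event with differing severity, which fits separate records. Protocol section 12.1 leaves data entry to eCRF completion guidelines that are not among the documents. The omission is therefore conditional. Equally, nothing requires a new record, so classification could differ between sites.

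A third tempting reading is that each missed event costs 8.3 points. That is the maximum for one child in one row. For the any-TEAE row, a single other TEAE over 48 to 96 weeks makes the shift zero.

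Finally, much worsening is captured elsewhere. Laboratory, vital-sign, ECG and ECHO changes are covered by their own rule. The physical-examination summary in SAP section 6.8.9 is a weaker backstop, because it excludes findings that occurred at screening and baseline.

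These points narrow the concern. What stands is the gap for symptom-based AEs that begin between consent and first dose, are ongoing at dosing and worsen on one record. If such an event becomes serious, it is still missing from the treatment-emergent SAE table.

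**Conclusion.** The concern holds in a limited form. The TEAE rule depends on start date alone and differs, without explanation, from the SAP's rule for measured abnormalities. The result is a less complete AE summary for the primary endpoint, provided that sites keep a worsened AE on a single record. The number affected is probably small, because only AEs ongoing at first dose are exposed, but the documents do not allow it to be estimated. The per-row limits of 8.3 and 16.7 points assume exactly 12 and 6 children in the denominators; the plan says approximately. The change is worth making because the rule is explicit and the remedy is cheap, not because a large bias has been shown.

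**What to change.** Change the definition in SAP section 5.7 so that a TEAE is an AE that starts, or worsens in severity or becomes serious, from initiation of the first dose through 28 days after the last dose. This matches the SAP's own approach to measured abnormalities.

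State in the SAP and the eCRF completion guidelines that an on-treatment worsening of a pre-dose AE is entered as a new AE record dated at the worsening. The pre-dose record should stay in the non-treatment-emergent listing, so that the worsening is counted once in the event totals of section 6.8.1. Align the partial-date rule in section 5.2.6 by applying it to the date of worsening as well.

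The cost is a few sentences in the SAP, an eCRF completion note and some data entry or queries for the few AEs ongoing at first dose. No new assessment is needed. Protocol section 11.4 does not ask for a worsening date, so for children already enrolled that date may have to be recovered from source records.
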